4. STUDY POPULATION SELECTION

4.1 Study Population

4.2 Inclusion Criteria

Subjects MUST meet all of the following criteria at the screening and baseline visits to enter into the study:

1. At least 18 years of age
2. Vision-loss attributed to clinically detectable ME associated with either CRVO or BRVO. Subjects may be treatment-naïve, or if previously-treated with a steroid, must have demonstrated response to treatment.
3. Duration of ME (defined as the time since initial diagnosis of ME) ≥ 9 months in subjects with CRVO and ≥ 12 months in subjects with BRVO. If both eyes are eligible, the study eye will be the eye with worse VA
4. Best-corrected visual acuity (BCVA) as measured by the ETDRS methodology of between 25 and 70 letters (+1.2 and +0.3 logMAR units or 20/320 and 20/40 Snellen equivalent) in the study eye
5. Retinal thickness in the central subfield (as measured by SD-OCT) of >290 μm (females) and >305 μm (males) if using a Cirrus (Zeiss) instrument, or if a Spectralis (Heidelberg) instrument is used, thickness should be >305 μm (females) or >320 μm (males) in the study eye
6. Be able to understand and willing to provide written informed consent
7. Be willing and able to adhere to the instructions set forth in the study protocol

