7.2 Intent-to-Treat

The intent-to-treat (ITT) population will include all subjects who received study medication. This population will be the primary population for efficacy analyses and will be used to summarize all efficacy variables and will summarize subjects as treated.

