13.2 SD-OCT, FA and FP

CRT measured by Cirrus (Zeiss) or Spectralis (Heidelberg) instrument will be summarized at each visit, using continuous summary statistics including change from baseline. Comparison between treatment groups for CRT will be performed using the same approaches as specified for BCVA in section 13.1.

Two time to event analyses for CRT of study eye as specified below will be evaluated using the same statistical method for the event of achieving a treatment response of ≥ 15 letters improvement from baseline in BCVA in section 12.1. The starting date of the evaluation will be the date of first dose. Results from unscheduled visits or early termination visits will be included in the time to event analysis.

- Time to resolution of macular edema: defined as first time point at which CRT is less than or equal to 315 μm for study eye.
- Time to loss of resolution of macular edema among treatment responders (population for this analysis includes subjects who achieved resolution of macular edema except on the last day of measurement): defined as first time point at which CRT returns to greater than 315 μm from first achieving the resolution of macular edema.

For the event of resolution of macular edema, subjects receiving rescue medication prior to or on the same date as the achievement of resolution of macular edema will be censored on the day of their rescue medication receipt. Subjects with neither rescue medications received, nor resolution of macular edema will be considered censored on the last date known to be rescue medication free and resolution of macular edema free. For the event of loss of resolution of macular edema after resolution achieved, subjects receiving rescue medications prior to the loss of resolution of macular edema will be considered censored on the day of rescue medication receipt and subjects receiving rescue medications on the same date as loss of macular edema will be considered for loss of macular edema. Subjects with neither loss of resolution of macular edema nor rescue medication received will be considered censored on the last date known to be loss of resolution of macular edema free and rescue medication free.

Total area of capillary non perfusion within ETDRS Grid (16DA) and total area of fluorescein leakage within the ETDRS grid assessed by FA using both Optos instruments (i.e ultra-widfield) and non-Optos (i.e widefield) will be summarized using continuous summary statistics.

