Table 14.2.1.1.3.4	Best Corrected Visual Acuity Letter Score (All Visits) – Categorical Summary (10-Letter or More Worsening)	ITT Population (Observed Case)
Table 14.2.1.2.1	Best Corrected Visual Acuity Letter Score - Continuous Summary	ITT Population (LOCF)
Table 14.2.1.2.2	Best Corrected Visual Acuity Letter Score – Continuous Summary	ITT Population (Observed Case)
Table 14.2.1.3	Time to Achievement of 15 Letters or More Improvement from Baseline in BCVA	ITT Population
Table 14.2.2.1.1	Spectral-Domain Optical Coherence Tomography (SD-OCT) Central Retinal Thickness (CRT)	ITT Population (LOCF)
Table 14.2.2.1.2	Spectral-Domain Optical Coherence Tomography (SD-OCT) Central Retinal Thickness (CRT)	ITT Population (Observed Case)
Table 14.2.2.2.1	Total Area of Capillary Non-perfusion and Total Area of Fluorescein Leakage within the ETDRS Grid (16DA) Assessed by FA and FP	ITT Population (Observed Case)
Table 14.2.2.2.2	Change in Fluorescein Leakage from Screening within the ETDRS Grid (16DA) Assessed by FA and FP	ITT Population
Table 14.2.2.3.1	Time to Resolution of Macular Edema ITT Population	ITT Population
Table 14.2.2.3.2	Time to Loss of Resolution of Macular Edema Among Treatment Responders ITT Population	ITT Population
Table 14.2.3	Time to Administration of Rescue Treatment	ITT Population

Table 14.3.1	Overall Summary of Treatment-Emergent Adverse Events by Treatment Group	Safety Population
Table 14.3.2	Ocular Treatment-Emergent Adverse Events by System Organ Class and Preferred Term	Safety Population
Table 14.3.3	Non-Ocular Treatment-Emergent Adverse Events by System Organ Class and Preferred Term	Safety Population
Table 14.3.4	Ocular Treatment-Emergent Adverse Events Related/Possibly Related to Study Medication by System Organ Class and Preferred Term	Safety Population
Table 14.3.5	Non-Ocular Treatment-Emergent Adverse Events Related/Possibly Related to Study Medication by System Organ Class and Preferred Term	Safety Population
Table 14.3.6	Ocular Treatment-Emergent Adverse Events Related/Possibly Related to Study Procedure by System Organ Class and Preferred Term	Safety Population
Table 14.3.7	Non-Ocular Treatment-Emergent Adverse Events Related/Possibly Related to Study Procedure by System Organ Class and Preferred Term	Safety Population
Table 14.3.8	Serious Treatment-Emergent Adverse Events by System Organ Class and Preferred Term	Safety Population

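### Resolution of macular edema (CRT ≤315 µm) carries no baseline condition, although the entry criteria admit eyes already at or below 315 µm

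*SAP*

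**What the plan says.** SAP section 13.2 adds two time-to-event analyses of study-eye CRT.

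- **Time to resolution of macular edema** is "defined as first time point at which CRT is less than or equal to 315" µm. One cut-off serves both sexes and both OCT instruments, and no fall from baseline is required. On timing, "The starting date of the evaluation will be the date of first dose".
- **Time to loss of resolution among treatment responders** is "defined as first time point at which CRT returns to greater than 315" µm after resolution was first achieved. The "population for this analysis includes subjects who achieved resolution of macular edema except on the last day of measurement".

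The table list in SAP section 20 assigns both analyses to the ITT population; the first is titled "Time to Resolution of Macular Edema ITT Population". SAP section 7.2 states: "The intent-to-treat (ITT) population will include all subjects who received study medication".

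Inclusion criterion 5 (protocol section 4.2), which must be met at screening and baseline, uses four limits. It asks for "Retinal thickness in the central subfield (as measured by SD-OCT) of >290" µm for women on Cirrus, with >305 µm for men. It continues "if a Spectralis (Heidelberg) instrument is used, thickness should be >305" µm for women, with >320 µm for men.

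**The concern.** Three of the four entry limits lie below the resolution cut-off, so an eye can be enrolled for macular edema while already meeting the SAP's definition of resolved edema. For that eye the event does not show improvement.

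The loss analysis inherits the problem. Its wording speaks of CRT returning above 315 µm, which presumes a start above 315 µm that the SAP never requires, and its responder set can contain eyes that did not respond. The BCVA response whose method section 13.2 borrows is a gain of at least 15 letters from baseline, so no eye can meet it at entry. The CRT version has no such safeguard.

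These results have a use. Protocol section 3.1 says efficacy signals will help decide which formulation goes forward, and section 3.2 names a long duration of effect as a feature of the optimal one. Time to loss of resolution bears directly on anatomical duration.

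**Working it through.** **Does any rule remove these eyes?** No. The baseline definition (SAP 8.3), the ITT definition (7.2), the censoring rules (13.2) and the list of changes from protocol (17) contain no baseline CRT exclusion.

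**Overlap by stratum** (cut-off 315 µm from SAP 13.2, limits from criterion 5, whole micrometres):

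| Stratum | Entry limit | 315 − limit | Eligible values ≤315 | Largest thickening from the lowest eligible value that still scores as resolved |
|---|---|---|---|---|
| Women, Cirrus | >290 | 25 | 291–315 | 315 − 291 = 24 |
| Men, Cirrus | >305 | 10 | 306–315 | 315 − 306 = 9 |
| Women, Spectralis | >305 | 10 | 306–315 | 315 − 306 = 9 |
| Men, Spectralis | >320 | −5 | none | none; a fall of at least 321 − 315 = 6 is needed |

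**Example.** A woman on Cirrus has 310 µm at baseline, 312 at Visit 4 (the first scheduled post-dose OCT) and 318 at Visit 5. She has a resolution event at Visit 4, enters the responder set, and has a loss event at Visit 5. Her retina only thickened. Had the Visit 4 scan been above 315 µm, it would not have been an event.

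**How many eyes?** The documents give no CRT distribution and no planning figure for this endpoint, so there is nothing of the plan's own to reproduce. I assumed lognormal baseline CRT, truncated at each entry limit L, with raw device values compared with 315 µm:

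P(baseline ≤315 | eligible) = [F(315) − F(L)] / [1 − F(L)]

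For a pre-truncation mean/SD of 400/130 µm, F(290) = 0.196, F(305) = 0.243 and F(315) = 0.276.

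- L = 290: 9.93%
- L = 305: 4.35%
- L = 320: 0
- Four equal strata: (9.93 + 4.35 + 4.35 + 0)/4 = 4.66%; × 20 = 0.93 eyes per arm; chance of at least one among 40 = 1 − (1 − 0.0466)^40 = 85%

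All seven assumed distributions:

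| Mean/SD (µm) | L = 290 | L = 305 | Four equal strata | Per arm of 20 | At least one in 40 |
|---|---|---|---|---|---|
| 400/100 | 9.08% | 4.12% | 4.33% | 0.87 | 83% |
| 400/130 | 9.93% | 4.35% | 4.66% | 0.93 | 85% |
| 450/130 | 5.70% | 2.56% | 2.70% | 0.54 | 67% |
| 500/150 | 3.45% | 1.56% | 1.64% | 0.33 | 48% |
| 550/180 | 2.46% | 1.11% | 1.17% | 0.23 | 37% |
| 500/100 | 0.88% | 0.45% | 0.44% | 0.09 | 16% |
| 550/100 | 0.11% | 0.06% | 0.06% | 0.01 | 2% |

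With other instrument mixes, half women:

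- All Cirrus: 0.08–7.1%, or 0.02–1.4 per arm; chance of at least one in 40 is 3–95%.
- All Spectralis: 0.03–2.2%, or 0.01–0.44 per arm; chance of at least one in 40 is 1–59%.

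**Weight of one eye.** In the resolution curve it is at most about 1/20 = 5 points. In the loss-of-resolution set it is 1/n: 1/15 = 6.7, 1/10 = 10 or 1/5 = 20 points for assumed responder numbers of 15, 10 or 5.

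**The case against.** The strongest reply is that the effect may be nil. Mean, SD, instrument mix and responder numbers are all assumed, and the largest shares need a population in which 24% of eyes lie below 305 µm before truncation. Even then, equal strata give less than one eye per arm. The percentages for at least one eye in 40 are chances of occurrence, not effect sizes. All of this stands.

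Second, assignment is 1:1 randomized and the limits and cut-off are the same in both arms, so such eyes are expected equally in each. What remains is chance imbalance of about one eye, not systematic bias. This also stands; the defect is in what the event means.

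Third, the stakes are low. The study is not powered for efficacy, its primary objective is safety, and continuous CRT summaries, plots and an SD-OCT listing are planned as well. That limits the severity. But the listing only lets a reader spot such an eye; it does not correct the curve or the responder set.

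Fourth, a filter at 315 µm leaves trivial crossings just above the line and drops genuine improvers, such as an eye going from 310 to 250 µm. Both are true and are counted under the cost of the fix. Keeping ITT as the main analysis with the restricted set as sensitivity would use the same two analyses in the opposite order.

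Finally, the Manual of Procedures is not available, and a conversion between devices would change the overlap.

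**Conclusion.** The concern holds. Followed as written, SAP 13.2 can score an unchanged or slightly thicker eye as resolved and then as a treatment responder, in three of the four sex-by-instrument strata. That conclusion follows from the text and needs no distributional assumption beyond CRT in the SAP being the central subfield thickness of criterion 5, in raw device units.

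The practical size is small and uncertain: possibly zero eyes, and under the assumed distributions at most about 1.4 per arm of 20 (all Cirrus). Only the two CRT time-to-event analyses are affected. The primary safety objective and the continuous CRT results are not. It should be fixed, because the error is in the definition and correcting it costs little.

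**What to change.** In SAP section 13.2, keep 315 µm but limit time to resolution, and the responder set for loss of resolution, to eyes with baseline CRT above 315 µm. Report the number excluded per arm, and keep the full ITT version as a sensitivity analysis. As a clarification only, state that post-dose scans alone can be events; the clock already starts at first dose.

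This costs a wording change and a filter on a value already collected. If no eye is affected, the results do not change. The downsides are:

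- A few eyes, possibly including genuine improvers, leave these two analyses, which then no longer cover the full ITT population. The loss would be uneven by stratum: with 400/130 and equal strata, 9.93/18.63 = 53% of excluded eyes would be women on Cirrus, and none would be men on Spectralis.
- An eye just above the line (316, then 314, then 318 µm) can still resolve and lose resolution on a very small change. Under the same assumptions with equal strata, 0.1–3.9% of eligible eyes (0.02–0.78 per arm) start above 315 and up to 325 µm. Replacing 315 µm by each eye's own entry limit would not avoid this: 0.1–4.4% (0.01–0.87 per arm) lie within 10 µm above their own limit.

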3.2 Rationale for Study Design and Control Group

While current treatment options for RVO are effective for many patients, the treatment burden is high. This study is designed to enable selection of the optimal AR-1105 formulation to continue with further clinical development. The optimal formulation will provide strong efficacy and a long duration of effect. The hypothesis is that a longer (>3 months) sustained release should necessitate less frequent intravitreal injections, and a lower steroid dose would potentially result in fewer, or less-frequent steroid-associated AEs without compromising effectiveness. Taken together these attributes would reduce the burden of treatment. The study is designed to inform decisions on further development of AR-1105 as safely and efficiently as possible.

[figure not shown]

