A linear model with change from baseline BCVA letters for study eye only as the response, baseline BCVA letters as a covariate, and treatment group as a main effect will be fit to determine treatment group effect with separate models completed for each follow-up visit. These analyses will be used to determine differences in formulations and may be used to assess whether there are differences in outcomes between subjects' data pre- and post-interim to determine whether the data may be pooled. Subjects who receive rescue medication prior to the summarized visit will have their measure replaced with their last observation prior to receiving rescue medication. The least squares mean, standard error, and CI for each treatment group, and the difference between treatment groups will be presented for

study eye only. Additionally, analyses will be completed using individual two-sample t-tests and 90% and 95% CIs around the difference between treatment groups in mean BCVA and mean change from baseline BCVA for study eye only.

Median time (in months) to achieve a treatment response of ≥ 15 letters improvement from baseline in BCVA for study eye and median time (in months) to rescue therapy will be estimated using Kaplan-Meier methods with 90% and 95% CI, calculated using the method of Brookmeyer and Crowley (1982). The log rank statistic will be used to determine differences in time to achieve response between the two treatment groups to determine differences in formulations. Cox proportional hazards will also be used to analyze time to event, including baseline BCVA as a covariate. Results from unscheduled visits or early termination visits will be included in the time to event analysis.

For the event of achieving a treatment response of ≥ 15 letters improvement from baseline in BCVA for study eye, the starting date will be the date of first dose. Subjects receiving rescue medications prior to or on the same date as the achievement of improvement will be considered censored on the day of rescue medication receipt; subjects with neither rescue medications received nor improvement achieved will be considered censored on the last date known to be rescue medication free and improvement achievement free. For the event of receiving rescue therapy, the starting date for the time to event evaluation will be the date of first dose. Subjects who do not receive rescue therapy will be considered censored on the last date known to be event free.

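### SAP 13.2 compares CF1 with CF2 on loss of edema resolution only among eyes that resolved, so the SAP's only measure of how long resolution lasts is not a randomised comparison

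*SAP*

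**What the plan says.** SAP 13.2 defines two CRT events in the study eye.

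- **Resolution.** "Time to resolution of macular edema: defined as first time point at which CRT is less than or equal to 315" µm.
- **Loss of resolution.** CRT goes back above that threshold, worded as "from first achieving the resolution of macular edema". For this event the "population for this analysis includes subjects who achieved resolution of macular edema except on the last day of measurement".

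Both events "will be evaluated using the same statistical method for the event of achieving a treatment response" on BCVA. The section cited for that method is 12.1. Section 12 covers residual implant and has no subsections, so 13.1 is evidently meant. There, "The log rank statistic will be used to determine differences in time to achieve response between the two treatment groups". A Cox model is also fitted, whose only covariate besides treatment is baseline BCVA. SAP 13.2 starts the clock at first dose for both CRT analyses.

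SAP Section 20 lists the output as Table 14.2.2.3.2. Its title says that it concerns responders, and its population column says ITT.

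Protocol 3.1 says that safety, tolerability and efficacy signals to Month 6 will decide which formulation goes forward. Protocol 3.2 adds: "The optimal formulation will provide strong efficacy and a long duration of effect".

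**The concern.** Membership of the analysis set is decided by a measurement taken after treatment. If one formulation resolves only the easier eyes and the other resolves those and some harder ones, the two responder groups hold different mixes of eyes. The 1:1 allocation balanced the groups as randomised, not these subsets. The Cox model does not repair this, because it has no term for baseline CRT, type of occlusion or duration of edema. Changing the time origin does not repair it either.

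What is at stake is one input to the choice of formulation. No other planned analysis measures how long resolution lasts, and long duration is a stated attribute of the formulation wanted.

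**Working it through.** **The plan's own figure.** The only sample-size figure is the 13.9% bound for an adverse event not seen in 20 subjects: 1 − 0.05^(1/20) = 0.139. It reproduces. It fixes about 20 eyes per arm and says nothing about durability.

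**Inputs from the documents.** About 20 eyes per arm, monthly CRT to Month 6, threshold 315 µm, eyes resolved only on the last day excluded, log-rank comparison.

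**Inputs assumed.** The documents give no resolution or relapse rates. Take easy and hard eyes, and let the monthly chance of losing resolution depend on the type of eye and not on the formulation. Easy eyes resolve equally often in both arms; formulation B resolves more hard eyes than A. There is then no true difference in durability within either type.

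**Hand check, central case.** 40% of eyes are hard. Easy eyes resolve in 90% in both arms, hard eyes in 20% on A and 80% on B. Monthly loss is 15% (easy) and 40% (hard). Let every responder resolve at Month 1, so that both time origins give the same comparison.

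- Responders: A 20 × (0.60×0.90 + 0.40×0.20) = 12.4; B 20 × (0.60×0.90 + 0.40×0.80) = 17.2.
- Hard eyes among responders: A 0.08/0.62 = 13%; B 0.32/0.86 = 37%.
- Lost by Month 6 (five monthly chances): easy 1 − 0.85^5 = 0.556; hard 1 − 0.60^5 = 0.922. Among responders, A 0.871×0.556 + 0.129×0.922 = 0.60; B 0.628×0.556 + 0.372×0.922 = 0.69.
- Mean months in resolution per resolved eye: easy (1 − 0.85^6)/0.15 = 4.152; hard (1 − 0.60^6)/0.40 = 2.383.
- Responders only: A (0.54×4.152 + 0.08×2.383)/0.62 = 3.92; B (0.54×4.152 + 0.32×2.383)/0.86 = 3.49.
- All eyes, never resolved = 0: A 0.54×4.152 + 0.08×2.383 = 2.43; B 0.54×4.152 + 0.32×2.383 = 3.00.

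B is behind among responders and ahead over all eyes, although no resolved eye keeps its resolution for a shorter time because it received B. The one-step log-rank hazard ratio for loss, exp[(O − E)/V], is 1.33 (B/A).

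**Range, by simulation.** Here the month of resolution varies, so the time origin matters. The milder case has hard eyes resolving in 40% v 80%, with loss 15%/30%. The stronger case has 50% hard eyes, resolving in 10% v 90%, with loss 10%/50%.

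| Case | Responders of 20, A v B | Hard share | HR from first dose | HR from first resolution | Months resolved, all eyes, A v B |
|---|---|---|---|---|---|
| Milder | 14.0 v 17.2 | 23% v 37% | 1.10 | 1.13 | 2.56 v 3.00 |
| Central | 12.4 v 17.2 | 13% v 37% | 1.26 | 1.32 | 2.30 v 2.85 |
| Stronger | 10.0 v 18.0 | 10% v 50% | 1.89 | 2.01 | 2.07 v 2.84 |

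**Controls.** If hard eyes resolve equally often in both arms, the hazard ratio is 1.00. If hard eyes lose resolution at the same rate as easy ones, it is 1.00 from first resolution and 0.96 from first dose. Both conditions are needed for the bias.

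**Effect on the test.** With 20 per arm and the clock from first resolution, the log-rank is significant against B in 4%, 8% and 23% of trials (milder, central, stronger), against 2.5% nominal. Power for a true hazard ratio of 2 is about Φ(½√d × ln 2 − 1.96): 19% with d = 10 loss events and 34% with d = 20. The bias would enter the decision mainly through estimates and curves rather than p-values.

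**The case against.** The strongest reply is about weight. Efficacy is unpowered and meant to inform later studies. The analysis is openly titled as one among responders, and how long responders hold their response is a fair descriptive question. All of that stands, and it limits the grade. It does not justify a between-formulation test on this subset.

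A reader might infer four stronger things that the documents do not support.

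- **That nothing else anatomical bears on durability.** SAP 13.2 compares CRT between formulations by the 13.1 methods, SAP 13 lists CRT change at Months 1 to 6, and the tables use the ITT population. Time to rescue also covers all treated eyes. These bear on persistence of effect; they do not measure how long resolution lasts.
- **That the planned test would reverse a true advantage.** Suppose A holds 8 easy eyes for 4 months and 12 hard eyes for 1 month, while B holds 8 easy eyes for 3 months and never resolves hard ones. Responder medians reverse (1 v 3 months). The log-rank does not: expected losses on A are 12×20/28 + 8×8/16 + 8×8/8 = 20.6 against 20 observed (chi-square 0.13, p = 0.72). The Cox hazard ratio for loss, A/B, is 0.81. The tests lean towards A, so the caution must cover medians as well as tests.
- **That the responder analysis hides most of the benefit.** Take assumed response rates of 86% v 60% and 3.9 v 3.6 months resolved among responders. The all-eyes gap is 0.86×3.9 − 0.60×3.6 = 1.19 months. Of this, 0.26 × 3.75 = 0.98 (82%) is response rate, which time to resolution already reports in all treated eyes.
- **That this analysis is the selection rule.** Protocol 3.1 uses safety, tolerability and efficacy signals together.

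**Conclusion.** The concern holds as a cheap improvement to a secondary analysis. That the comparison is not protected by randomisation follows from the text alone. The direction of bias is conditional: the formulations must differ in which eyes they resolve, and harder eyes must relapse sooner. The bias then counts against the formulation that resolves more hard eyes. Its size rests wholly on assumed rates: a spurious hazard ratio for loss of 1.10 to 1.89 from first dose, or 1.13 to 2.01 from first resolution. It is near 1.0 if either condition is absent. These are one-step log-rank estimates, without the Cox adjustment for baseline BCVA.

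**What to change.** In SAP 13.2:

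1. Make the between-formulation durability comparison in all treated eyes of the randomised phase. Use months (or scheduled visits) with CRT ≤315 µm up to Month 6, counted as 0 for eyes that never resolve and as not in resolution after rescue. The latter matches the failure rule in 13.1. Report the mean difference with 90% and 95% intervals and a Wilcoxon test.
2. State how missed visits and dropout are handled. For example, give the proportion of observed visits in resolution and, separately, count missing as not resolved, in line with the SAP's observed-case and failure approaches.
3. Exclude, or analyse separately, eyes with baseline CRT ≤315 µm. Inclusion criterion 5 admits CRT above 290 or 305 µm for women on either instrument and men on Cirrus, so such eyes could count as resolved without a response. Baseline CRT precedes treatment, so this exclusion does not bring back the selection problem.
4. Keep the responder-only Kaplan-Meier curve and median as description per formulation, labelled as a non-randomised comparison, without a log-rank test or hazard ratio.
5. Correct the population label of Table 14.2.2.3.2.

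The cost is one derived variable from monthly CRT already collected, plus wording; no new procedures. The downside is small: the all-eyes measure combines speed, chance and length of response, so it should be read beside time to resolution.
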